#### 10.4.3 ANALYSIS OF THE SECONDARY ENDPOINT(S)

See above.

---

#### 10.4.4 SAFETY ANALYSES

All adverse events will be recorded once per condition for each subject, calculated dichotomously based on its emergence during the treatment timeframe. These outcomes will be presented in tables for review by the DSMB, and such outcomes will be accompanied by descriptive and inferential statistics (both mean levels and change from baseline in each condition) to determine whether AEs and changes in AEs are more likely to occur in the experimental condition.

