## 8 ASSESSMENT OF SAFETY

The safety of the study and its participants (as described in 2.3.1) will be monitored via (1) Supervising clinicians [name]. (hormone-related AEs) and [name]. (mood and suicide-related AEs) as well as (2) a Data and Safety Monitoring Board (DSMB).

AEs will be assessed daily during the telephone contacts in the two administration conditions, and will be assessed weekly at laboratory visits. All AEs will be reported immediately to the PI and [name], who will determine severity and next steps in consultation with the appropriate clinical supervisor ([name] for physical adverse events, [name] for psychological and behavioral adverse events).

The DSMB will evaluate AEs that are submitted during scheduled reviews. The North Carolina Translational and Clinical Sciences (NCTraCS) Data and Safety Monitoring Board (NCTraCS DSMB) has agreed to serve in this role. The Board is composed of MDs from a variety of disciplines, an R.N. from the UNC School of Nursing, a Biostatistician, a Regulatory Expert, and for purposes of this study, a psychiatrist or clinical psychologist may serve as an ad hoc member.

Although not expected given the doses and duration of hormone exposure, the DSMB will, during scheduled reviews, specifically evaluate the frequency of AEs related to the hormonal RCT. The DSMB will specify the tables and data it wishes to have presented to it at all meetings, including but not limited to, moderate to severe side effects and all serious adverse events. **DSMB review of this study will occur every six months.** At these meetings the DSMB will also review data from participants who have been discontinued by study staff or who have withdrawn or dropped out of the study, and the reasons for discontinuation. The DSMB will also identify if any study procedures should be altered or stopped in the event of an indication of harm to participants attributable to the study interventions. The DSMB will evaluate issues of participant safety as well as the adequacy and integrity of accumulating data, review of enrollment data, and making recommendations regarding safety.

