## 8.3 TIME PERIOD AND FREQUENCY FOR EVENT ASSESSMENT AND FOLLOW-UP

The occurrence of an AE or SAE may come to the attention of study personnel during study visits and interviews of a study participant. All AEs including local and systemic reactions not meeting the criteria for SAEs will be captured on the appropriate documentation. Information to be collected includes event description, time of onset, clinician's assessment of severity, relationship to study product (assessed only by those with the training and authority to make a diagnosis), and time of resolution/stabilization of the event. All AEs occurring while on study must be documented appropriately regardless of relationship. All AEs will be followed to adequate resolution.

Pre-existing medical conditions are exclusionary for participation in the trial, with the exception of psychiatric conditions. Any psychiatric condition or symptom that is present at the time that the participant is screened, including mood symptoms and suicidal *ideation*, will be considered as baseline and not reported as an AE. However, if the study participant's condition or symptom deteriorates significantly with regard to the severity or impact of the symptom on the participant's functioning or safety (as determined by Drs. [name], [name], [name], and [name]) at any time during the study, it will be recorded as an AE.

UPs will be recorded in the data collection system throughout the study.

Changes in the severity of an AE will be documented to allow an assessment of the duration of the event at each level of severity to be performed. AEs characterized as intermittent require documentation of onset and duration of each episode.

The PI will record all reportable events with start dates occurring any time after informed consent is obtained until 7 (for non-serious AEs) or 30 days (for SAEs) after the last day of study participation. At each phone call and study visit, study staff will inquire about the occurrence of AE/SAEs since the last visit. All AEs will be immediately (within 2 hours) reported to the PI, who will consult with Drs. [name], [name], and [name] in the 24 hours that follow. Events will be followed for outcome information until resolution or stabilization.

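### Section 10.4.4 promises to compare changes in adverse events, but its one yes/no emergence score per condition cannot show a physical side effect becoming worse or lasting longer on hormones

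*Combined protocol and SAP*

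**What the plan says.** Section 10.4.4 (Safety Analyses) sets the scoring unit: "All adverse events will be recorded once per condition for each subject, calculated dichotomously based on its emergence during the treatment timeframe". These outcomes go to the DSMB in tables, accompanied by "descriptive and inferential statistics (both mean levels and change from baseline in each condition"). The stated purpose is "to determine whether AEs and changes in AEs are more likely to occur in the experimental condition". The section names no severity scale, baseline, test or sidedness.

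The data collected are much richer:

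- **Frequency.** Section 8 says "AEs will be assessed daily during the telephone contacts in the two administration conditions, and will be assessed weekly at laboratory visits".
- **Severity and duration.** Section 8.3 records onset, severity and resolution, and adds: "Changes in the severity of an AE will be documented to allow an assessment of the duration of the event at each level of severity". Section 8.2.1 gives three grades: mild, moderate and severe.
- **A pre-agent record in each condition.** Section 7.3.3 lists side-effect and AE monitoring at every laboratory visit. Its timeline places the day +7 assessments at the visit where the first patch is applied.

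Three other provisions bear on the point. Section 8.3 records a significant deterioration of a pre-existing psychiatric symptom as an AE. Section 10.4.4 lists significant deterioration in mood and in suicidality as AEs to be monitored. Sections 8.5 and 10.4.7.1 test moderate, severe and serious AEs between conditions every six months at alpha .05.

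**The concern.** The safety comparison aims at changes in AEs, but the variable that it defines holds only presence or absence. Within a woman, one day of mild cramps and 14 days of severe cramps both score 1. If emergence means new onset, a headache already present at day +7 that becomes severe on agent scores 0. Section 8.3 collects duration at each grade for a stated purpose, yet no section analyses it.

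This matters because the placebo condition is the natural perimenstrual window, in which breast tenderness, cramps and headache may occur anyway. Against that background a hormone effect could take the form of worse or longer symptoms rather than symptoms in more women. A DSMB table built as Section 10.4.4 is written could then show little or no difference between conditions.

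**Working it through.** The documents give no power or error rate for the safety analysis, so there is no planned figure to reproduce.

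**1. What the score can carry.** Let Y(i,c) be 0 or 1 for woman i in condition c.

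- The mean of Y over women is an incidence proportion, not a severity level.
- Change from baseline needs a baseline value of Y, and none is defined. If emergent means absent at baseline, the baseline is 0 for every event and the change is Y itself.
- So "both mean levels and change from baseline in each condition" adds nothing about severity or duration when applied to this score.

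**2. Which women inform a paired yes/no comparison.** Let b be the number of women with the event on hormones only, and c the number on placebo only. The exact McNemar test uses only these b + c discordant women. With c = 0 its two-sided p-value is 2 × (1/2)^b. For b = 5 this is 0.0625 and for b = 6 it is 0.031, so at least six discordant women are needed. A symptom present in the same women in both conditions gives b = c = 0, whatever happens to its grade or duration.

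**3. Only severity changes.** Inputs: 30 completers (Section 10.5), three grades (Section 8.2.1) and two-sided .05. Assumptions:

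- 30%, 50% or 70% of women have the symptom in both conditions.
- The placebo grade is mild or moderate with equal chance.
- Random variation between conditions is one grade up or down, 10% each way.
- A share w of affected women rises one further grade on hormones, with grade kept within mild to severe.

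Power from 2,000 simulated trials per cell:

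| Women affected | Yes/no, any w | Sign test on grade, w = 30% | w = 50% | w = 70% |
|---|---|---|---|---|
| 30% | 0.00 | 0.06 | 0.24 | 0.52 |
| 50% | 0.00 | 0.28 | 0.67 | 0.92 |
| 70% | 0.00 | 0.52 | 0.90 | 0.99 |

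**4. Symptom days rise.** Assumptions: 30 women, 14 agent days, daily odds tripled on hormones, and woman and woman-by-condition SDs of 1.0 on the logit scale. The documents give no placebo incidence, so 20% to 90% is shown.

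| Placebo incidence over 14 days | 20% | 30% | 50% | 70% | 90% |
|---|---|---|---|---|---|
| Yes/no (McNemar) | 29% | 36% | 36% | 29% | 3% |
| Signed-rank on days | 43% | 61% | 78% | 87% | 92% |

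Repeat runs agree to within a few percentage points. With a woman-by-condition SD of 2.0 the yes/no test has 14–20% power (2% at 90% incidence), against 26–44% for days. With no effect, harm-direction error was 0.3–1.6% for yes/no and 1.2–2.6% for days, against a nominal 2.5%.

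**5. Incidence itself rises.** Exact McNemar power with 30 women, for within-woman correlation from 0 to 0.4 (capped where 0.4 is not attainable):

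| Placebo v hormones | Power |
|---|---|
| 50% v 70% | 0.26–0.38 |
| 50% v 79% | 0.55–0.79 |
| 50% v 90% | 0.90–0.99 |
| 70% v 90% | 0.36–0.51 |

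The detectable excess is capped at 1 minus the placebo rate, but it is not zero.

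**6. Incidence rises and duration does not.** Assumptions: duration uniform on 1–14 days and independent conditions. Here the yes/no test does better than signed-rank on days: 0.59 v 0.54 (20% to 50%), 0.61 v 0.43 (50% to 80%) and 0.90 v 0.69 (50% to 90%).

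**The case against.** Four stronger readings are tempting, and the documents do not support them.

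- **That the plan throws severity away.** It does not do so everywhere. The six-monthly test is restricted to moderate, severe and serious AEs. Under Section 8 the DSMB chooses its own tables, including moderate to severe side effects, and Section 10.4.10 lets it request individual data. These routes use grade as a threshold or depend on a request. None supplies an analysis of duration or a rule for a pre-existing physical symptom.
- **That worsening always scores zero.** Emergence is undefined, and new onset is only its ordinary sense. For the outcomes most central to this trial the inference fails, because significant deterioration in mood or suicidality is itself an AE.
- **That a symptom common under placebo can show no excess.** This holds only when severity or duration alone changes. Step 5 shows useful power when incidence rises.
- **That symptom days should replace incidence.** Step 6 shows the yes/no comparison doing better when more women get a symptom of unchanged duration. The day-count gain in step 4 follows from assuming tripled daily odds. That assumption implies incidences on hormones of about 39%, 52%, 73%, 87% and 97%, whereas the highest side-effect rates listed for the agents are 29% (estradiol) and 20–30% (progesterone).

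It is also fair to say that Section 10.4.4 names changes in AEs as a target, so the authors did not intend to ignore worsening. That is correct as to intent. But the statistics are attached to the dichotomous outcomes, and no other variable is defined.

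**Conclusion.** The point holds as an internal inconsistency with a limited consequence. Section 10.4.4 sets out to compare changes in AEs using a score that cannot measure them. It leaves undecided how worsening of a physical symptom already present at day +7 is counted, and it leaves the severity and duration records out of the comparison.

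A pure rise in grade in women who have the symptom in both conditions gives the yes/no score zero power by construction. What a graded comparison recovers ranges from very little (0.06) to nearly everything (0.99). That range rests on assumed rates, since no placebo rate is given for any symptom. The conclusion covers the listed physical side effects. It does not extend to mood or suicidality, and it does not show that the yes/no comparison is the wrong test for new side effects.

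**What to change.** In Section 10.4.4:

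1. Keep the paired yes/no incidence comparison. Define an event as either new onset or a rise in grade from the pre-agent day +7 report in that condition, and state that this report is taken before the first patch and pill.
2. For the listed physical side effects, add two paired summaries per woman from existing records: worst grade relative to day +7, and days with the symptom in each condition. Compare conditions with a paired signed-rank test and interval, labelled as supportive.
3. Make the change-from-baseline wording refer to the grade summary and its day +7 baseline, and name the test and sidedness for the yes/no comparison.

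This needs protocol wording and more tabulation, but no new data. It adds unadjusted safety comparisons, and Section 10.4.9 makes no multiplicity provision, so they should be read descriptively. The halting and stopping rules stay as they are.

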**Assessment of Outcomes.** Participants will complete phone measures of symptoms and suicidality starting on the first day of patches/pills and ending 5 days following the last patch/pill (phone symbols in figure above). Three lab sessions will measure mediating constructs using behavioral tasks. In each condition, lab visits will occur on days +7, +14, and +22 following ovulation.

**Primary Windows of Comparison for Hypothesis Testing.** To test whether prevention of E2/P4 withdrawal is associated with mediating behavioral constructs and suicide risk, we will compare tasks and interviews in **LABPL2** with **LABEXP2**.

**Blinding of Participants and Staff.** All study staff performing assessments will remain blinded to condition. The natural within-woman variation in menstrual cycle length from one cycle to another will help maintain the participant blind. Few women have regular 28 day cycles, and between-cycle variation up to 8 days is normal. Demand characteristics regarding the impact of hormonal manipulation will be minimized by informing participants that women vary a great deal in their responses to hormones, and our current evidence does not allow us to predict for certain whether hormones have a positive, negative, or neutral effect on women's symptoms (of note, this is scientifically accurate). Finally, although some women may become unblinded later in the extended hormone phase, work by the mentoring team suggests that pharmacologic delay of menses does not influence the course of perimenstrual mood symptoms.

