#### 6.1.9 DURATION OF THERAPY

The planned duration of active treatment is 14 days. All days in which participants use patches and pills will be utilized in multilevel modeling analyses, which accommodate unbalanced/missing data.

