## 7.2 LABORATORY PROCEDURES/EVALUATIONS

### 7.2.1 CLINICAL LABORATORY EVALUATIONS

A point-of-care urine **pregnancy test** will be completed in our laboratory on site on two occasions: prior to randomization at the enrollment visit, and at the third study visit of the first condition.

At all 6 laboratory assessments during active treatment with placebo or E2/P4, women will provide 10ml **blood samples** to be assayed for E2/P4 to evaluate the success of the hormone in achieving stable luteal phase levels of E2/P4. [name]'s laboratory at UNC will conduct assays. Storage onsite will be handled by medical technician [name] in [name] laboratory.

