**Follow-Up Timeline:**

**Condition 1 (Follow-Up Visits 1-3):**

- Negative Pregnancy Test Confirmed at Enrollment
- Ovulation Testing
- Positive Ovulation Test #1= Day 0
- Study Followup Visits 1-3 Scheduled for days +7, +14, +22
- Study Followup Visit 1 (Day +7): Assessments, administration of study agent patch A and dispensation of pills (**Condition 1**)
- Study Followup Visit 2 (Day +14): Assessments, replacement of study agent patch A with patch B (**Condition 1**)
- Removal of study patch and end of pills on day +21
- Study Followup Visit 3 (Day +22): Assessments, Pregnancy Test

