### 10.4 DESCRIPTION OF STATISTICAL METHODS

#### 10.4.1 GENERAL APPROACH

The design of this study is a two-period crossover design, where each of two study periods is a perimenstrual frame of the menstrual cycle (days +7 to +22 following ovulation where positive ovulation test day=0). Each participant will complete both conditions in a randomized order.

The primary windows of comparison will be the final seven days of each administration phase, which will allow for a comparison of a woman's mean scores in the placebo condition compared to her mean scores in the experimental condition.

Primary hypothesis tests will be evaluated using a alpha level of .05, with a two-tailed test.

All outcomes will be checked for normality; given the low likelihood that suicidality will follow a normal distribution even in this clinical sample, we expect that we will need to utilize nonparametric procedures.

---

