***Below, we list the adverse events that are most likely to occur in the course of the study***

***and will therefore be monitored most closely (at every daily and weekly participant contact during administration of study agents). However, participants will have the opportunity to report any other adverse event in addition to those listed below.***

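### The per-condition adverse event window is undefined; if it means days on agent, it counts withdrawal under placebo but not the delayed withdrawal after active agent

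*Combined protocol and SAP*

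**What the plan says.** Section 10.4.4 records each AE once per condition, "calculated dichotomously based on its emergence during the treatment timeframe". It gives no start day, stop day or rule for an event that begins after the agent stops. Other sections point to different windows:

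- **Days on agent, +7 to +21.** Section 6.1.9: "The planned duration of active treatment is 14 days". The Section 7.3.3 timeline: "Removal of study patch and end of pills on day +21". Section 10.4.4 ties its closest AE monitoring to contacts "at every daily and weekly participant contact during administration of study agents". Section 5.5 explains its relatedness term for serious AEs as new onset while on patches or pills; Sections 8.5 and 10.4.7.1 repeat the rule without that explanation.
- **To day +22.** Section 7.2.1 places blood sampling "At all 6 laboratory assessments during active treatment with placebo or E2/P4", which includes the day +22 visit. Section 10.4.1 sets the study period as "days +7 to +22 following ovulation where positive ovulation test day=0".
- **To about day +26.** Section 8: "AEs will be assessed daily during the telephone contacts in the two administration conditions". Section 4.1 runs those calls from the first day of agent, "ending 5 days following the last patch/pill".
- **Whole study.** Section 8.3 records AEs to 7 days (non-serious) or 30 days (serious) after the last day of participation, without assigning them to a condition.

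Section 10.4.4 lists significant deterioration in mood and in suicidality among the AEs to be followed. Sections 5.5, 8.5 and 10.4.7.1 have the between-condition AE difference tested every six months at .05 and sent to the DSMB. Section 10.1 says there will be no formal SAP.

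**The concern.** The two conditions place hormone withdrawal at different times. Section 2.2 says the 14 agent days cover the time when natural withdrawal would occur, so under placebo it falls inside an on-agent window. Under active agent those days are, by design, an extended luteal phase (Section 4.1). Withdrawal is then delayed rather than removed (Section 2.3.1), and the risk is described as shifted (Section 4.1, Participant Safety). Section 7.3.4 adds a final visit partly because of risk after exogenous hormones stop.

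If withdrawal raises mood and suicidality AEs, which is the trial's hypothesis, an on-agent window counts them under placebo and leaves out their counterpart under active agent. A difference in timing would then look like a safety advantage, and worsening after the agent stops would be missing from the comparison that the DSMB receives.

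**Working it through.** The plan states no rate or power for the AE comparison, so there is no figure to reproduce. The check has three parts.

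**1. Day count.** On agent: 21 − 7 = 14 days. Calls: from day +7 to 21 + 5 = day +26, which is 20 days inclusive per condition and 40 in all. The payment schedule in Section 5.3 agrees: $200 at $5 per day is 40 days. So about five post-agent days per condition are already observed by telephone but lie outside an on-agent window.

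**2. Size of the tilt (all rates assumed).** Let b be background risk, w withdrawal risk, and f the share of withdrawal inside the window.

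In-window risk = 1 − (1 − b)(1 − w·f)

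Under placebo, f = 1. Under active agent, withdrawal is assumed to start after day +21 and to spread evenly over L = 7 to 10 days, so f = (end day − 21)/L:

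- end +21: f = 0
- end +22: f = 1/7 = .143 or 1/10 = .10
- end +26: f = 5/7 = .714 or 5/10 = .50

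Total risk is set equal in both conditions, so the true odds ratio (OR, active vs placebo) is 1. Placebo risk is 1 − .98 × .98 = .0396 for b = w = .02, and 1 − .95 × .90 = .145 for b = .05, w = .10. Gaps are fewer women with an AE under active agent, per 30 (the completer target in Section 10.5). Ranges run over L.

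| Window ends | b = .02, w = .02: active risk; OR; gap | b = .05, w = .10: active risk; OR; gap |
|---|---|---|
| +21 | .0200; 0.49; 0.6 | .0500; 0.31; 2.9 |
| +22 | .0220–.0228; 0.54–0.57; 0.5 | .0595–.0636; 0.37–0.40; 2.4–2.6 |
| +26 | .0298–.0340; 0.74–0.85; 0.2–0.3 | .0975–.1179; 0.64–0.79; 0.8–1.4 |

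The first column is meant for severe or serious AEs and the second for a test that includes moderate ones.

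Sensitivity:
- If only 75% of natural withdrawal falls in the placebo window, the day +21 ORs become 0.57 and 0.38.
- If b is scaled by 20/14 for the longer window, the day +26 ORs become 0.79–0.88 and 0.68–0.81.
- If 90% of post-agent withdrawal risk falls in the first five days, the day +26 ORs (b unscaled) are 0.95 and 0.92.

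**3. A masked excess, and the power to see it.** Suppose withdrawal risk after active agent were double that under placebo. Total active risk is 1 − .98 × .96 = .0592 (true OR 1.53) or 1 − .95 × .80 = .240 (true OR 1.86). The day +21 window still shows 0.49 and 0.31, because none of the excess is counted. The day +26 window shows 1.00–1.22 and 1.00–1.34.

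With an exact McNemar test (30 pairs, two-sided .05, independence within woman assumed), even a complete window would find this excess only 0.2% of the time (.0592 vs .0396) or 8% (.240 vs .145).

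**The case against.** **Little effect on decisions.** The DSMB considers termination only if the active condition shows greater risk of severe or serious AEs and there is evidence of causality. A result falsely favouring the agent triggers nothing, and the trial makes no efficacy claim. Harm needs a real post-agent excess, whereas Section 2.3.1 expects none beyond natural withdrawal. Even a doubled risk would almost never be detected at the rates above. This stands, and it limits the point to the fairness of tables and estimates.

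**Data are collected anyway.** Onset time is recorded (Section 8.3), AEs are asked about at each call, and the DSMB may specify its tables and will define its data elements (Sections 8 and 8.6). So a reader should not infer that late events are lost or individual reports impaired. But none of this text sets the window, and no SAP is promised that would.

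**On-agent counting is a legitimate comparison.** It covers the same cycle days in both conditions and suits hormone side effects, which this point leaves untouched. Calling equal total risk an OR of 1 presupposes interest in agent plus washout. Reporting both windows answers this.

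**The model is crude.** Constant background and evenly spread withdrawal probably overstate the residual tilt at day +26, as the sensitivity figures show. Larger claims are also possible: with 5% background and withdrawal risks of 20% or 30%, an on-agent window would give a significant result falsely favouring the agent 39.8% or 73.6% of the time. The documents do not support such rates. Section 5.1 does not expect shifts to reach crisis level, and Section 8.3 counts baseline symptoms only if they deteriorate significantly.

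**Conclusion.** The AE window is undefined, and its best-supported reading biases the mood and suicidality comparison in the agent's favour. That reading is inferred; the documents do not establish that on-agent days will be used. Under the daily-call reading the tilt is much smaller but may remain. The direction depends on withdrawal raising these AEs, as the trial hypothesises, and on withdrawal after active agent being delayed, as the protocol states.

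The size is unknown. The odds ratios are illustrations on assumed rates; at the severe or serious level they amount to less than one woman in 30. A reader might infer that the six-monthly test would otherwise catch a harmful agent, or that a termination decision is likely to change. Neither follows: the test has almost no power at these rates under any window. What is at stake is whether the DSMB sees unbiased tables and estimates, including any worsening after the agent stops.

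**What to change.** In Section 10.4.4:

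- Define one day-numbered AE window, identical in both conditions, from first patch to at least the last daily call (five days after the last patch or pill, about day +26).
- Assign AEs that start after agent to the preceding condition.
- Report on-agent, post-agent and combined AEs by condition. Use the combined window for the mood and suicidality comparison, including the six-monthly tests, and keep the on-agent comparison for hormone side effects.
- State that five post-agent days may not capture all withdrawal (5/7 = 71% of a 7-day and 5/10 = 50% of a 10-day withdrawal, if evenly spread), so some tilt may remain.
- Carry the same definition into the data elements set under Section 8.6.

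The cost is a few lines of text and one extra table split, since the calls, AE questions and onset times already exist. The combined window slightly dilutes on-agent contrasts, which the split keeps visible. No dose, schedule or clinical rule changes.
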